### 5.9.2 Pharmacokinetic Parameters and Anti-drug Antibody Analyses

The PK parameters derived using non-compartmental techniques will be regarded as primary endpoints for the PK analyses (see Section 5.9.1). Primary inference for all the PK parameters will be based on the PKAP population.

The concentration at each time point will be summarized as arithmetic mean, standard deviation, median, minimum, and maximum, number of BLQs (Below the Limit of Quantification). Pharmacokinetic parameters using geometric means will be compared to determine when steady state conditions are achieved during the treatment period. Geometric means and between-subject coefficients of variation (CVb) will be calculated for loge-transformed AUC0-28d, Ctrough and Cmax where:

Geometric mean = exp(mean on log scale)

CVb (%) = sqrt[exp(SD) - 1] x 100

– where SD is the standard deviation of the loge-transformed data.

Following loge-transformation, Ctrough will be analyzed using analysis of variance (ANOVA), the model will include time and subject as a fixed effect. The residual variance from the model will be used to calculate point estimates and 90% CIs for the least squares means for each treatment formulation on the loge scale. These estimates will be back transformed to give point estimates and 90% CIs on the original scale.

The potential relationship between plasma concentrations of nemolizumab and change in pruritus NRS, biomarkers or other indicators of disease activity will be explored using PK/PD modeling, as appropriate.

Incidence of positive ADA results will be summarized by treatment group (absolute occurrence and percent of subjects). Individual PK profiles of subjects with or without ADA will be plotted to explore ADA impact on systemic exposure levels.

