1.3 Pharmacokinetic profile

PK profile of Nemolizumab was investigated in two clinical studies (Phase 1: CIM001JP; and Phase 2a in AD patient: CIM003 J Gin which single doses from 0.1 to 3 mg/kg, or repeated doses of 0.1 mg/kg, 0.5 mg/kg or 2.0 mg/kg Q4W, or 2 mg/kg Q8W were studied. PK assessment after subcutaneous injections of mg/kg doses showed a dose proportional increase of nemolizumab serum concentrations after single and repeated dose administrations. The terminal elimination half-life of nemolizumab was around 2 weeks after single and repeated administrations. Steady state concentrations were achieved from week 16 of treatment and limited systemic accumulation was observed after repeated administrations. The systemic exposure to nemolizumab appeared to be slightly lower in AD subjects compared to healthy volunteers (AUC ratios ranging from 0.63 to 0.92).

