## 4 INVESTIGATIONAL PLAN

### 4.1 Overall Study Design and Plan

This is a randomized, placebo-controlled, double-blinded, parallel group, multicenter study to evaluate the safety and efficacy of nemolizumab in patients suffering from PN. Approximately 70 adult patients suffering from PN for at least 6 months with severe pruritus defined by the mean of the worst daily intensity of the NRS score  $\geq 7$  over the previous week at baseline will be randomized in the study. Subjects meeting inclusion/exclusion criteria will be randomized in a 1:1 ratio to nemolizumab or placebo. Each subject will receive three subcutaneous injections of 0.5mg/kg of nemolizumab or matching placebo. Injections will be administered every 4 weeks (at baseline, week 4 & week 8).

Subjects' participation in the study will be up to 22 weeks, including an up to 4-week screening period, a 12-week treatment period (last study drug injection at week 8) and a 6-week follow-up period (10 weeks after the last study drug injection corresponding to 5 half-lives of nemolizumab).

Assessments of efficacy, safety, PK, PD, and biophysical will be conducted throughout this clinical trial. Refer to Appendix 1 for the complete schedule of assessments.

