  - $AUC_{0-t}$ : area under the concentration time curve calculated by the mixed linear logarithmic trapezoidal method from  $T_0$  up to the sampling time corresponding to the last quantifiable concentration ( $C_{last}$ )

From week 12 to week 18 (or Early termination or Unscheduled visit, if applicable):

- $t_{1/2}$ : the terminal half-life value ( $t_{1/2}$ ) will be calculated using the equation  $\ln 2/k$  after the last drug injection (week 8).
- $AUC_{0-t}$ : area under the concentration time curve calculated by the mixed linear logarithmic trapezoidal method from  $T_0$  up to the sampling time corresponding to the last quantifiable concentration ( $C_{last}$ ).
- $AUC_{0-\infty}$ : Area under the plasma concentration-time curve calculated by the mixed linear logarithmic trapezoidal method from  $T_0$  and extrapolated to time infinity as:  $AUC_{0-\infty} = AUC_{0-t} + C_{last} / k_{el}$ . When the extrapolation represents more than 20%,  $AUC_{0-\infty}$  and  $t_{1/2}$  will not be reported.

At weeks 4, 8, 12, 16, 18 (or Early termination or Unscheduled visit if applicable):

- $C_{trough}$ : The residual drug concentration
- Accumulation index: calculated with the serum nemolizumab trough concentration obtained 4 weeks after the first dose (week 4) and 4 weeks after last drug injection (week 18).

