## 5.10 Determination of Sample Size

For the current study, it is assumed that the common standard deviation is 35 and that the true difference between Nemolizumab and the placebo is 30% in terms of percent change from baseline in worst itching score on a NRS at Week 4.

With an effect size of  $(30/35=) 0.857$ , a power of 90% and a type I error of 5% two-sided; at least 30 subjects are needed per group. In order to maintain the power of the tests, for per-protocol population, in case of drop outs/major deviations at Week 4, the sample size will be increased to 35 subjects per group, i.e. 70 to be randomized.

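### The planned 90% CIs for mean Ctrough leave out between-subject variance, so they are not valid 90% intervals for the mean trough in PN patients

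*SAP*

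**What the plan says.** SAP 5.9.2 log-transforms Ctrough and fits an ANOVA in which "the model will include time and subject as a fixed effect". It continues: "The residual variance from the model will be used to calculate point estimates and 90% CIs for the least squares means". The means are described as belonging to each treatment formulation, and the results are back-transformed to the original scale. Protocol 9.2.5 has the same text.

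Three other statements bear on the point:

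- The stated use of the comparison in SAP 5.9.2 is steady state: "Pharmacokinetic parameters using geometric means will be compared to determine when steady state conditions are achieved during the treatment period".
- The same section reports "Geometric means and between-subject coefficients of variation" for AUC, Ctrough and Cmax, as descriptive statistics.
- SAP 5.9.1 defines Ctrough at five scheduled times: "At weeks 4, 8, 12, 16, 18 (or Early termination or Unscheduled visit if applicable". SAP 5.9.2 does not say which of them enter the ANOVA.

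**The concern.** A confidence interval around a geometric mean trough is normally read as a statement about the patient population. That needs an error term containing the variation between patients. Here subject is a fixed effect, so differences between patients are absorbed by the subject terms and only the scatter left over reaches the interval.

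The paragraph reads like a crossover bioequivalence template, in which each subject receives each formulation and the interest is in a within-subject ratio. This trial has one active product, parallel groups and no treatment term in the Ctrough model. The only means the model can produce are means per sampling week. The text also says that residual variance yields the point estimates, which it does not.

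At stake is a stated secondary objective, characterising nemolizumab PK in PN. SAP 5.9.2 treats the non-compartmental PK parameters as the primary endpoints of the PK analysis. Reported troughs would carry 90% limits that do not have 90% coverage, and these would sit beside a between-subject CV with which they do not agree.

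**Working it through.** **Figures to reproduce.** None. The documents give no Ctrough interval, between-subject CV (CVb) or within-subject CV (CVw).

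**Inputs from the documents.** Model terms and error variance: SAP 5.9.2. Ctrough weeks 4, 8, 12, 16 and 18: SAP 5.9.1. Active-arm size: "the sample size will be increased to 35 subjects per group" (SAP 5.10). For the PK illustration only: "The terminal elimination half-life of nemolizumab was around 2 weeks after single and repeated administrations" (protocol 1.3) and "Injections will be administered every 4 weeks (at baseline, week 4 & week 8" (SAP 4.1).

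**Assumptions.** All CVs. For the constant-offset calculation, 33 of the 35 subjects contribute and each has the same log-scale offset at every week.

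**Formulas.** On the log scale s² = ln(1 + CV²). With n subjects and T weeks:

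- planned SE of a weekly mean = √(s²w / n), with (n−1)(T−1) degrees of freedom
- SE for the population mean = √((s²b + s²w) / n)
- ratio of the two = √(1 + s²b / s²w)
- approximate coverage of the planned 90% CI = 2Φ(t / ratio) − 1

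The planned SE formula was checked against an ordinary least squares fit of one simulated dataset (n = 35, T = 5): 0.03311 both ways.

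**Worked case: CVb 40%, CVw 20%, n = 33, T = 3.**

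- s²b = ln(1.16) = 0.1484; s²w = ln(1.04) = 0.0392.
- Planned: SE = √(0.0392/33) = 0.0345; t with 64 df = 1.669; half-width 0.0575, a factor of 1.06 either way.
- Population: SE = √(0.1876/33) = 0.0754; t with 32 df = 1.694; half-width 0.1277, a factor of 1.14 either way.
- Ratio = √(1 + 0.1484/0.0392) = 2.19. Coverage = 2Φ(1.669/2.19) − 1 ≈ 55%. Simulation also gives about 55%, and an interval on total variance covers 90%.

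**Range over assumed CVs (n = 33, T = 3).**

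| CVb | CVw | SE ratio | Coverage of planned 90% CI |
|---|---|---|---|
| 20% | 40% | 1.12 | about 86% |
| 30% | 30% | 1.41 | about 76% |
| 40% | 20% | 2.19 | about 55% |
| 30% | 15% | 2.21 | about 55% |
| 60% | 15% | 3.85 | about 33% |

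**Contrasts between weeks.** The subject offset cancels in a difference of two weekly means, so its variance is 2s²w/n. Under the constant-offset assumption the residual variance is then the right error term, and simulated coverage is about 90%.

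**Five-week model.** A constant offset is doubtful once Weeks 16 and 18 enter. They fall 8 and 10 weeks after the last injection at Week 8, which is 4 and 5 half-lives at 2 weeks each, so differences in elimination rate spread subjects apart and inflate the pooled residual. The illustration is a one-compartment subcutaneous model with a 14-day half-life, three doses 28 days apart and n = 35. Assumed CVs are clearance 20-40%, volume 20-30% and residual 10-30%.

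| Week | True SE / planned SE, five weeks pooled |
|---|---|
| 4 | 0.8-0.9 |
| 8 | 1.0-1.1 |
| 12 | 1.0-1.2 |
| 16 | 2.1-2.4 |
| 18 | 2.6-3.0 |

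In the same illustration with Weeks 4, 8 and 12 only, the ratio is 1.6-3.9 and coverage 33-68%.

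**The case against.** The strongest defence is that the only comparison SAP 5.9.2 names is between times, to find when steady state is reached. Residual variance with subject in the model is the natural error term for that. This stands for contrasts, but the plan attaches its intervals to the least squares means themselves and specifies none for a difference or ratio between weeks.

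Second, between-subject spread is not hidden. The geometric mean and CVb are reported for Ctrough, so a reader could rebuild a population interval from them and n. That limits the harm but does not correct the interval that is printed.

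Third, a reader might infer that every planned interval is far too narrow. The documents do not support this. They give no variance components, and with a low CVb and high CVw the shortfall is slight. They also do not restrict the ANOVA to the three visits that end a dosing interval. With all five weeks pooled, the illustration puts Weeks 4-12 about right, with Week 4 slightly too wide. This part of the objection stands in full.

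Fourth, no passage plans to compare these intervals with another population or to base a dose decision on them. Exposure-response is left to separate PK/PD modelling. This also stands.

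**Conclusion.** The defect is one of specification and needs no assumed figure: between-subject variance is missing from the error term, so these are not valid 90% intervals for the mean trough in PN patients. Its size does rest on assumptions. With a constant subject effect, coverage could be anywhere from near nominal to about one third. With five weeks pooled, the error is concentrated at Weeks 16 and 18.

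That the intervals are too wide at one week and too narrow at another, depending on which weeks enter, is itself a reason not to use one pooled residual for all of them. In the pooled case the inflated residual would also make early contrasts such as Week 8 against Week 4 too wide.

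A reader might go further and infer that the steady-state assessment or the efficacy result is undermined. Neither follows: the steady-state question rests on contrasts, and no efficacy conclusion uses these intervals. The impact is confined to a secondary PK output.

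**What to change.** In SAP 5.9.2, and in protocol 9.2.5 if it is amended:

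- Fit log Ctrough by a mixed model with week fixed and an unstructured covariance across weeks. A random subject effect is enough if only Weeks 4, 8 and 12 are used.
- Name the weeks that enter the model.
- Report the geometric mean per week with a 90% CI from that model.
- For steady state, report week-to-week trough ratios (Week 8/Week 4, Week 12/Week 8) with within-subject 90% CIs.
- Delete the reference to each treatment formulation, which matches no term in the model, and the statement that residual variance gives the point estimates.

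The cost is one model statement and a few lines of text. No new data are needed, and some reported intervals become wider.

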### 5.9.3 Pharmacodynamic Analyses

Primary inference for all biomarker analyses based on blood and skin samples (D-Squames and skin biopsies) will be based on the observed cases. All biomarker variables (using logarithm transformation) will be summarized across treatments at each time point.

Any observations in trends within the Biomarker data may be explored with PK/PD correlations/models. All of this analysis will be considered exploratory. The outputs will be in a separate report.

The detailed analysis will be carried out by Biomarker group in GALDERMA, and will be reported separately.

TP-GDO-WW-016-07  
Effective Date: 05 Sep 2018  
Related to: SOP-GDO-WW-019

CONFIDENTIAL

Project Document Version No. 2.0  
Project Document Effective Date: Date of last signature  
Page 48 of 59

## 5.10 Determination of Sample Size

For the current study, it is assumed that the common standard deviation is 35 and that the true difference between Nemolizumab and the placebo is 30% in terms of percent change from baseline in worst itching score on a NRS at Week 4.

With an effect size of  $(30/35=) 0.857$ , a power of 90% and a type I error of 5% two-sided; at least 30 subjects are needed per group. In order to maintain the power of the tests, for per-protocol population, in case of drop outs/major deviations at Week 4, the sample size will be increased to 35 subjects per group, i.e. 70 to be randomized.

## 5.11 Changes in the Conduct of the Study or Planned Analysis

Changes in the conduct of the study may be instituted through a protocol amendment. Planned analyses will be revised as appropriate. Similarly, planned analyses may be changed as a result of planned blinded data reviews. Changes will be finalized prior to database lock.

The ridit score is calculated combining data in the atopy and country stratum due to small sample size in each strata. The Placebo group is used as the reference group to calculate mean ridit score of the nemolizumab group using the method described in Uwawunkonye et. al. paper.

**Appendix 1 Schedule of assessments****Table 2 Schedule of Assessments**

Study period	Screening period (Day -28 to Day-1)		Treatment period							Observation period/ Follow up		Early termination (E/T) or Unscheduled visit (if applicable)	
	Visit Week	V1 Screening 1	V2 screening 2	V3 Baseline Day 1	V4 W1 Day 8	V5 W2 Day 15	V6 W4 Day 29	V7 W8 Day 57	V8 W12 Day 85	V9 W16 D113	V10 W18 Day 126		
		D-28 to D-8	Day-7 (a)		Day 1	±1 day	±2 days	±2 days	±2 days				
ICF and when applicable country specific consent form		•											
Photo Consent and Biopsies consent form (if applicable)		•											
Demographics		•											
Medical history/ Previous therapies and procedures		•											
Inclusion/Exclusion criteria		•		•									
Concomitant therapies and procedures		•	•	•	•	•	•	•	•	•	•	•	
Height				•									
Weight				•				•	•				
Blood sample for serology (HIV, Hepatitis B and C test)		•											
Blood samples for specific IgE		•											
Blood samples for TB test (b)		•											
SAFETY ASSESSMENTS													
Vital signs		•		•	•	•	•	•	•	•	•	•	
Physical exam		•		•		•	•	•	•	•	•	•	
Blood samples for hematology and biochemistry (c)			•	•		•		•				•	
Blood sample for CPK (d)		•		•		•	•	•				•	
Urinalysis			•	•		•	•	•	•			•	
12-lead ECG		•			•			•				•	
Pregnancy test (e)		Serum		Urine			Urine	Urine	Urine	Urine	Urine	Urine	
Respiratory assessment (f)		•	•	•	•	•	•	•	•	•	•	•	
Adverse Events		•	•	•	•	•	•	•	•	•	•	•	
STUDY DRUG													
Randomization				•									
Subcutaneous study drug injection				•			•	•					

(a) Screening visit 2 must be performed at least 7 days prior to Day 1 visit. Eligible subjects according to safety assessments will be provided with the Actigraphy and ePro devices.

(b) In case of indeterminate result for TB test, the test should be repeated at Scr 2 in the local laboratory (only one retest is allowed). If the test is still indeterminate, the subject must not be included in the study

(c) Blood samples for hematology and biochemistry must be performed in fasting conditions

(d) In case elevated CPK > 1.5 ULN at screening 1, the test will be repeated at screening 2. If the result is still abnormal, the subject will not be included. V7/W8 CPK applicable only to France

(e) Only for female of childbearing potential. Serum pregnancy test to be performed at screening visit 1 and urine pregnancy test (UPT) for all other visits. UPT should have a sensitivity threshold of less than 25mIU/mL. There should be at least 14 days between the serum pregnancy test at screening and the UPT at baseline.

(f) Respiratory assessments for all subjects, but PEF will be measured only for subjects with medical history of asthma

Study period Visit Week Day Visit window	Screening period (Day -28 to Day-1)		Treatment period							Observation period/ Follow up		Early termination (E/T) or Unscheduled visit (if applicable)
	V1 Screening 1 D-28 to D-8	V2 screening 2 Day-7 (a) Day 1	V3 Baseline Day 1 ±1 day	V4 W1 Day 8 ±2 days	V5 W2 Day 15 ±2 days	V6 W4 Day 29 ±2 days	V7 W8 Day 57 ±2 days	V8 W12 Day 85 ±5 days	V9 W16 D113 ±5 days	V10 W18 Day 126 ±7 days		
	EFFICACY/ PATIENTS REPORTED OUTCOMES											
	NRS (g)	•	Once daily by the subject at home in the evening until Day 126									•
VRS (g)			Once daily by the subject at home in the evening until Day 126									•
Sleep disturbance NRS (h)			Once daily by the subject at home in the morning until Day 29									
DPS (i)			•			•						
DLQI			•			•			•			•
Prurigo Assessment Scale (PAS)			•			•		•	•		•	•
IGA			•			•		•	•		•	•
PK AND ADA ASSESSMENTS												
Blood sample for PK			•	•	•	•	•	•	•	•	•	•
Blood sample for ADA			•		•	•	•	•	•	•	•	•
PHARMACODYNAMIC ASSESSMENTS												
Blood sample for biomarkers			•			•			•			
D-Squares samples			•			•			•			
4-mm skin biopsies (j)			•					•				
Control of biopsies healing (k)				•					•			
BIOPHYSICAL ASSESSMENTS												
Photos of whole body (l)			•			•		•	•		•	
Actigraphy			Every day until Day 29									
Exit Form											•	

(g) NRS and VRS must be performed by the subject at home using the device provided by the site once daily in the evening from screening 2 to the last visit.  
 (h) NRS for sleep disturbance must be performed by the subject at home using the device provided by the site once daily in the morning from screening 2 to Day 29.  
 (i) DPS must be performed by the subject at home following instruction provided by the Nurse on site and then subject should record DPS 24, 48 & 72 hrs after the 1st injection and at week 4 before the injection.  
 (j) Skin biopsies will be performed on lesional and non lesional skin at baseline and on lesional skin at week 12 only for patients consenting to have skin biopsies.  
 (k) When applicable, biopsies healing should be checked 2 weeks after skin biopsies  
 (l) Only for selected equipped sites – at least a Baseline & Week 12; Week 4, week 8 & week 18 if possible.

**Appendix 2 Criteria for potentially clinically significant vital signs and weight****Pulse rate**

$\leq 50$  bpm and decrease from baseline  $\geq 20$  bpm

$\geq 120$  bpm and increase from baseline  $\geq 20$  bpm

To be applied for all positions (including missing).

**SBP**

$\leq 95$  mmHg and decrease from baseline  $\geq 20$  mmHg

$\geq 160$  mmHg and increase from baseline  $\geq 20$  mmHg

To be applied for all positions (including missing).

**DBP**

$\leq 45$  mmHg and decrease from baseline  $\geq 10$  mmHg

$\geq 110$  mmHg and increase from baseline  $\geq 10$  mmHg

To be applied for all positions (including missing).

**Weight**

$\geq 5\%$  increase from baseline

$\geq 5\%$  decrease from baseline

### Appendix 3 Dermatology Life Quality Index (DLQI)

The DLQI questionnaire is designed for use in adults, i.e. subjects over the age of 16. It is self-explanatory and can be simply handed to the subject who is asked to fill it in without the need for detailed explanation. It is usually completed in one to two minutes.

#### Scoring

The scoring of each question is as follows:

Response	Score
Very much	scored 3
A lot	scored 2
A little	scored 1
Not at all	scored 0
Not relevant	scored 0
Question unanswered	scored 0
Question 7: "prevented work or studying"	scored 3

The DLQI is calculated by summing the score of each question resulting in a maximum of 30 and a minimum of 0. The higher the score, the more quality of life is impaired. The DLQI can also be expressed as a percentage of the maximum possible score of 30.

**\*\*Please Note:** That the scores associated with the different answers should not be printed on the DLQI itself, as this might cause bias\*\*

#### Meaning of DLQI Scores

0-1 = no effect at all on subject's life

2-5 = small effect on subject's life

6-10 = moderate effect on subject's life

11-20 = very large effect on subject's life  
 21-30 = extremely large effect on subject's life

#### **Detailed analysis of the DLQI**

The DLQI can be analyzed under six headings as follows:

Section	Questions	Score
Symptoms and feelings	Questions 1 and 2	Score maximum 6
Daily activities	Questions 3 and 4	Score maximum 6
Leisure	Questions 5 and 6	Score maximum 6
Work and School	Question 7	Score maximum 3
Personal relationships	Questions 8 and 9	Score maximum 6
Treatment	Question 10	Score maximum 3

The scores for each of these sections can also be expressed as a percentage of either 6 or 3.

#### **Interpretation of incorrectly completed questionnaires**

There is a very high success rate of accurate completion of the DLQI. However, sometimes subjects do make mistakes.

- If one question is left unanswered this is scored 0 and the scores are summed and expressed as usual out of a maximum of 30.
- If two or more questions are left unanswered the questionnaire is not scored.
- If question 7 is answered 'yes' this is scored 3. If question 7 is answered 'no' but then either 'a lot' or 'a little' is ticked this is then scored 2 or 1. If "Not relevant" is ticked, the score for Question 7 is 0. If it is answered 'no', but the second half is left incomplete, the score will remain 0.
- If two or more response options are ticked, the response option with the highest score should be recorded.
- If there is a response between two tick boxes, the lower of the two score options should be recorded.

- The DLQI can be analyzed by calculating the score for each of its six sub-scales (see above). When using sub-scales, if the answer to one question in a sub-scale is missing, that sub-scale should not be scored.

